8.5.4 Analysis of Secondary Efficacy Endpoint(s)

8.5.4.1 RGI-C responder

The proportion of RGI-C responder (subjects with a mean RGI-C global score $\geq +2.0$) will be summarized for each treatment group at Week 40 and Week 64. At Week 40 analysis, a logistic regression model will be applied with treatment group and baseline age stratification factor as independent variables, baseline RSS total score as a continuous covariate. The stratification factor of baseline RSS total score will not be included in the model.

At Week 64 analysis, a similar repeated measures logistic regression model will be applied including both Week 40 and Week 64 data as dependent variable, treatment group, study visit, interaction between treatment group and study visit, and baseline age stratification

factor as independent variables, baseline RSS total score as a continuous covariate. The stratification factor of baseline RSS total score will not be included in the model. The odds ratio comparing KRN23 treatment to conventional therapy will be provided along with 95% CI and p-value. The estimated responder rate and its 95% CI within individual treatment groups will also be provided.

8.5.4.2 RSS scores

The change from baseline in RSS (total, knee and wrist) scores over time will be analyzed using the same method as that of the RGI-C score. At Week 40 analysis, an ANCOVA model will be applied with treatment group and baseline age stratification factor as independent variables, baseline RSS total score as a continuous covariate. The stratification factor of baseline RSS total score will not be included in the model. At Week 64 analysis, a GEE model will be used with all RSS change from baseline data as dependent variable, treatment group, study visit, interaction between treatment group and study visit, and baseline age stratification factor as independent variables, baseline RSS total score as a continuous covariate. The stratification factor of baseline RSS total score will not be included in the model. The estimated difference between KRN23 treatment and active control group will be provided along with 95% CI and p-value. The estimated change from baseline in RSS score and its 95% CI within individual treatment groups will also be provided.

Descriptive statistics for all RSS scores and change from baseline in RSS score will be provided in both continuous and categorical summary. A listing of RSS scores for each subject will be provided. Graphic displays of RSS scores over time will also be provided by treatment group.

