4.6 Potential Covariate(s)

Unless specified otherwise, the randomization stratification factor (RSS total score ≤ 2.5 vs > 2.5) and age (< 5 vs ≥ 5) will be included as independent variables in the model for efficacy analysis. Region (Japan vs. rest of World) is used for randomization for operational and logistic considerations and will not be used as covariates in any analyses. For the GEE and ANCOVA analyses, baseline result of the response variable will be included as the covariate.

Other potential covariates such as gender might be used in growth analyses. If the baseline RSS total score or age is to be used in the statistical model as a continuous covariate, the corresponding randomization stratification factor will not be included in the same model. Refer to Section 8 for the details of statistical models and covariates for each efficacy endpoint.303, 304

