8.5.3 Analysis of Primary Efficacy Endpoint

The primary efficacy endpoint will be tested to compare the mean RGI-C global score between the KRN23 and active control groups.

At Week 40 analysis, an Analysis of Covariance (ANCOVA) model will be applied on the RGI-C global score with treatment group and baseline age stratification factor as independent variables, baseline RSS total score as a continuous covariate. The stratification factor of baseline RSS total score will not be included in the model.

For RGI-C knee, wrist and lower limb deformity scores, a similar ANCOVA model will be applied with baseline RSS wrist score used in RGI-C wrist score modeling and baseline RSS knee score used in RGI-C knee score and lower limb deformity score modeling.

At Week 64 analysis, RGI-C (global, knee, wrist and long leg) scores over time including Week 40 will be analyzed using GEE model that includes treatment group, visit, treatment group by visit interaction, baseline age stratification factor as independent variables, baseline RSS total score as a continuous covariate. The stratification factor of baseline RSS total score will not be included in the model.

The estimated difference of RGI-C between KRN23 treatment and active control group will be provided along with 95% CI and p-value. The estimated RGI-C score and its 95% CI within individual treatment groups will also be provided. Descriptive statistics for all RGI-C scores will be provided in both continuous and categorical summary. Summary of abnormality at baseline and change in abnormality at Week 40 and Week 64 will also be provided. A listing of RGI-C scores will be provided for each subject. Graphic displays of RGI-C scores will also be provided over time by treatment group.

If subjects receive orthopedic surgeries before week 40 X-ray visit, a sensitivity analysis will be performed by excluding these subjects from week 40 and week 64 RGI-C analyses. If subjects receive orthopedic surgery after week 40 but before week 64 X-ray visit, a sensitivity analysis will be performed at week 64 RGI-C analysis, where the week 40 RGI-C data will be used to impute Week 64 data for these subjects.

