8.5.4.3 Growth

Growth in standing height/recumbent length and weight will be summarized over time in observed value, Z-score and percentile. Individual subject growth curves will be plotted with CDC growth charts as reference.

For standing height/recumbent length Z-score, the GEE model will be used to assess the difference between treatment groups. Treatment group and baseline RSS stratification factor will be included as independent variables, baseline age and height/length Z score will be included as continuous covariates. The mid-parental height Z score will be calculated by averaging the height Z scores of parents and may also be considered as a covariate in the model. The stratification factor of baseline age will not be included in the model. The estimated difference between KRN23 treatment and active control group will be provided along with 95% CI and p-value. The estimated change from baseline and its 95% CI within individual treatment groups will also be provided.

The growth velocity defined in Section 5.7.3 will be estimated for selected pre-treatment period (e.g. within 1.5 years prior to baseline) and post-treatment period from baseline to Week 40 and from baseline to Week 64 respectively for each subject. If a subject has both

recumbent length and standing height measurements from 1.5 years prior to baseline to post-baseline period, the recumbent length will be subtracted by 0.8 cm before pooling with standing height data (<https://www.cdc.gov/nccdphp/dnpao/growthcharts/resources/sas.htm>).

An ANCOVA model will be applied on the change in growth velocity Z score from baseline to Week 40 or Week 64 to assess the difference between treatment groups. Treatment group and baseline RSS total score stratification factor will be included as independent variables, baseline Z score and age will be included as continuous covariates. The stratification factor of baseline age will not be included in the model. The estimated difference between KRN23 treatment and active control group will be provided along with 95% CI and p-value. The estimated change from baseline and its 95% CI within individual treatment groups will also be provided.

In addition, descriptive statistics of sitting height during the post-treatment period and its respective change from baseline will be provided by study visits. A listing of standing height/recumbent length and the respective Z score, percentile, growth velocity and sitting height will be provided.

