8.5.4.4 Walking Ability (6MWT)

For subjects ≥ 5 years of age at the screening visit, summary statistics of total distance walked and percent of predicted 6MWT will be tabulated for each study visit for the observed measures and their respective change from baseline based on the Full Analysis Subset (Baseline age ≥ 5 years). Change from baseline of total distance walked and percent of predicted 6MWT will be assessed using the GEE approach as outlined in Section 8.5.1 with baseline measures and baseline RSS total score stratification factor included as independent variables.

A listing containing the 6MWT details will be provided. Graphs showing change in total distance walked during 6MWT and percent of predicted 6MWT will be provided by treatment group.

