8.5.4.7 PD Analysis

The PD parameters will include serum phosphorus, TmP/GFR, serum 1,25(OH)₂D, TRP, and ALP. All PD analyses will be performed on the PD Analysis Set, unless stated otherwise.

Descriptive statistics of PD parameters and their respective change from baseline and percentage change from baseline will be tabulated by treatment group at each study visit.

The change in serum phosphorus from baseline to mean post-baseline values (average of Week 1, 4, 8, 16, 24, 32 and 40 serum phosphorus for Week 40 analysis and Week 1, 4, 8, 16, 24, 32, 40, 52 and 64 serum phosphorus for Week 64 analysis) will be analyzed using an ANCOVA model. Treatment group, baseline age and RSS total score stratification factors will be included as independent variables, baseline serum phosphorus will be included as a continuous covariate. The estimated difference between KRN23 treatment and active control group will be provided along with 95% CI and p-value. The estimated change from baseline within individual treatment groups will also be provided.

PD endpoints at all scheduled visits will be assessed using the GEE approach as outlined in Section 8.5.1 with change from baseline value as dependent variable, baseline measures and baseline age and RSS total score stratification factors included as independent variables.

The proportion of subjects achieving the normal range (3.2-6.1 mg/dL) will be reported by treatment group at each study visit. Similarly, proportion of subjects achieving TmP/GFR within the normal range (2.6 – 4.4 mg/dL) will be reported by treatment group at each study visit.

A listing containing PD parameters such as serum phosphate level, serum 1,25(OH)₂D, TmP/GFR, TRP, and ALP will be provided for each subject.

Graphs showing the change over time in PD parameters for both observed measure and the respective change from baseline will be provided by treatment group.

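### SAP 8.5.4.2 adjusts change in RSS knee and RSS wrist for baseline RSS total instead of the matching regional baseline, without a stated reason (minor)

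*SAP*

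**What the plan says.** SAP 8.5.4.2 handles RSS total, knee and wrist together: "change from baseline in RSS (total, knee and wrist) scores over time will be analyzed using the same method as that of the RGI-C score". It then writes out the models. At Week 40 (ANCOVA) and at Week 64 (GEE) the RSS covariate is baseline RSS total, entered as a continuous variable, beside treatment and the age stratum. No regional baseline is named.

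SAP 4.6 gives the general rule for GEE and ANCOVA models: the "baseline result of the response variable will be included as the covariate". The same section ends by deferring to the detailed text: "Refer to Section 8 for the details of statistical models and covariates for each efficacy endpoint".

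SAP 8.5.3, which 8.5.4.2 says it follows, uses regional covariates for the regional RGI-C scores at Week 40: RSS wrist for the wrist score, and "baseline RSS knee score used in RGI-C knee score and lower limb deformity score modeling".

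SAP 4.2.2 ranks change in RSS wrist and knee among the other secondary endpoints. Protocol 7.6.2.2 lists only RSS total.

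**The concern.** For RSS total, the named covariate is the response's own baseline. For RSS knee and RSS wrist it is the sum of the two regions, so the general rule in 4.6 is met for one of the three scores and missed for two.

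The sum is a weak stand-in. On the scoring form in SAP Appendix 4, a child with a total of 2.0, the minimum for entry, can have wrist 0 and knee 2.0, or wrist 2.0 and knee 0. The first child's wrist score cannot fall; the second's can fall by 2 points. The model treats them as equal at baseline.

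At stake are the estimates, confidence intervals and p-values that 8.5.4.2 promises for the two regional scores. With the total held fixed, a chance excess of baseline knee severity in one arm is an equal deficit of wrist severity. That imbalance stays in both regional estimates.

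**Working it through.** **1. Consistency of the text.** Covariates named for the modelled change-from-baseline endpoints:

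| Endpoint | SAP section | Baseline covariate |
|---|---|---|
| Height/length Z | 8.5.4.3 | own: "baseline age and height/length Z score will be included as continuous covariates" |
| Growth velocity Z | 8.5.4.3 | own |
| 6MWT, PROMIS, FPS-R | 8.5.4.4 to 8.5.4.6 | own: "baseline measures and baseline RSS total score stratification factor included as independent variables" (same in all three) |
| Mean serum phosphorus | 8.5.4.7 | own: "baseline serum phosphorus will be included as a continuous covariate" |
| Other PD, ALP | 8.5.4.7 | own |
| RSS total | 8.5.4.2 | own |
| RSS knee, RSS wrist | 8.5.4.2 | RSS total |

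The last row is the only exception. RGI-C scores are ratings of change with no baseline value of their own, so they are not counter-examples.

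**2. The plan's own figure.** SAP 3.5 gives 60 children and about 80% power for RGI-C global. A t-test with difference 0.40, SD 0.50 and two-sided 5% needs 26 per arm; 26/0.9 rounds up to 29, or 58 in total, which agrees with 60. With 30 less 10%, 27 per arm (54) are evaluable. The point below changes none of this. The plan states no figure for the regional models.

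**3. Assumed inputs.** The documents give no regional SDs, slopes or correlations. Assumed: baseline knee SD 0.7, wrist SD 0.6, wrist-knee correlation *r* of 0, 0.3 or 0.6, own-baseline slope *b* = 0.5 in size, residual SD 0.45 (variance 0.2025). Let *c* be the slope on the other region.

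**4. Formulas.** With the total fixed, the other region equals total minus own. Hence:
- residual variance adjusting for own baseline = 0.2025 + *c*² × Var(other | own), where Var(other | own) = SD² of the other region × (1 − *r*²);
- residual variance adjusting for total = 0.2025 + (*b* − *c*)² × Var(own | total).

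The SE ratio is the square root of the second over the first. At *r* = 0, Var(knee | total) = 0.49 − 0.49²/0.85 = 0.2075, and the value for wrist is the same.

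**5. Only the own region predicts (*c* = 0).**

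| *r* | Var(region given total) | SE ratio, total vs own | Worth, of 54 children |
|---|---|---|---|
| 0 | 0.2075 | √(1 + 0.25 × 0.2075/0.2025) = 1.121 | 54 × (1 − 1/1.256) = 11 |
| 0.3 | 0.146 | 1.086 | 8 |
| 0.6 | 0.083 | 1.050 | 5 |

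Over slopes of 0.25 to 0.75 and residual SDs of 0.35 to 0.6 the excess runs from 0.7% to 40%. At slope zero it is nil.

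**6. The other region also predicts.** At *c* = 0.25*b* the excess is 1.6 to 5.5%. The two models tie when (1 − *c*/*b*)/(*c*/*b*) = √(Var(other | own)/Var(own | total)). For knee at *r* = 0 this is √(0.36/0.2075) = 1.317, so *c*/*b* = 0.43. Across both regions and all three correlations the tie lies at 0.34 to 0.43. At *c* = 0.5*b*, knee, *r* = 0: total gives 0.2025 + 0.0625 × 0.2075 = 0.2155, own gives 0.2025 + 0.0625 × 0.36 = 0.2250, and the ratio is √(0.2155/0.2250) = 0.979. Over the three correlations, RSS total is then better by 2.1 to 2.6% (knee) and 3.3 to 4.2% (wrist).

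**7. Chance imbalance (*c* = 0).** The knee estimates under the two adjustments differ with SD of about √(2/27 × 0.25 × 0.2075) = 0.062 points at *r* = 0 (simulated range over the correlations 0.04 to 0.07), against an own-baseline SE of about 0.125. If knee and wrist residuals are independent, adjusting for total makes the two regional estimates correlated: −0.0519/(0.2025 + 0.0519) = −0.20 at *r* = 0, and −0.09 at *r* = 0.6. A positive residual correlation of 0.0519/0.2025 = 0.26 (*r* = 0) or 0.10 (*r* = 0.6) removes it.

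**8. Validity.** Simulated Week 40 ANCOVAs (27 per arm, 6000 per correlation, entry rule applied) gave bias of at most 0.002 points and type I error of 4.8 to 5.6% under total adjustment (Monte Carlo SE 0.3%). The entry rule did not alter the SE inflation.

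**The case against.** The strongest reply is that nothing is ambiguous. SAP 4.6 hands covariate detail to Section 8, and 8.5.4.2 names all three scores and prints the covariate for both analyses. That stands: RSS total would probably be programmed. What remains is an unexplained exception, in a section that also claims to follow a method whose Week 40 regional models do use regional baselines.

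The endpoints also rank low. The SAP adds them to the protocol's list and makes no multiplicity adjustment, so no formal decision depends on them. That stands and sets the severity.

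Third, the direction of the precision effect depends on undocumented inputs: RSS total contains the regional baseline and wins if the other region predicts strongly enough. That stands too. A reader might infer that precision is certainly lost, or that knee and wrist results will be pushed apart. The first needs the other region's slope to be below about 0.34 to 0.43 of the own slope; the second needs nearly independent residuals within a child.

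A reader might also infer that the RGI-C models need the same change, because SAP 8.5.3 moves from regional RSS at Week 40 to RSS total at Week 64: "At Week 64 analysis, RGI-C (global, knee, wrist and long leg) scores over time including Week 40 will be analyzed using GEE model", with RSS total as covariate for all four scores. The documents do not support prescribing one. RSS total fits the adjustment for baseline rickets severity in Protocol 7.6.4, and nothing shows that RSS knee predicts the long leg score better. That switch is at most a request for clarification.

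**Conclusion.** The inconsistency is real and the point is minor. Change in RSS knee and wrist is the one modelled change-from-baseline analysis not adjusted for its own baseline, and no reason is given. The cost is chance regional imbalance left uncorrected and probably some precision. How much is not known from the documents: under the assumed SDs, slope and residual SD, the SE is 5 to 12% larger if only the own region predicts, equal at a slope ratio of 0.34 to 0.43, and 2 to 4% smaller at 0.5.

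A stronger reading, that the regional effects would be biased or their tests invalid, is not supported: the covariate is a prespecified baseline variable in a randomised comparison, and the simulation showed neither problem. The primary RGI-C global test, RSS total, the sample size and the stated power are unaffected.

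**What to change.** In SAP 8.5.4.2, for both the Week 40 ANCOVA and the Week 64 GEE, replace the covariate wording with: *baseline RSS total, knee or wrist score, matching the response, as a continuous covariate*. If RSS total is intended for the regional scores, state the reason.

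If the multiple imputation in SAP 8.5.2 is applied to knee or wrist scores, add the matching regional baseline to its predictors, which now name only RSS total among the RSS scores.

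The cost is SAP wording and the matching program line. The regional scores are already collected, and one covariate replaces another, so no degrees of freedom are used. No change to the Week 64 RGI-C covariates in 8.5.3 is asked for here.

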8.5.4.3 Growth

Growth in standing height/recumbent length and weight will be summarized over time in observed value, Z-score and percentile. Individual subject growth curves will be plotted with CDC growth charts as reference.

For standing height/recumbent length Z-score, the GEE model will be used to assess the difference between treatment groups. Treatment group and baseline RSS stratification factor will be included as independent variables, baseline age and height/length Z score will be included as continuous covariates. The mid-parental height Z score will be calculated by averaging the height Z scores of parents and may also be considered as a covariate in the model. The stratification factor of baseline age will not be included in the model. The estimated difference between KRN23 treatment and active control group will be provided along with 95% CI and p-value. The estimated change from baseline and its 95% CI within individual treatment groups will also be provided.

The growth velocity defined in Section 5.7.3 will be estimated for selected pre-treatment period (e.g. within 1.5 years prior to baseline) and post-treatment period from baseline to Week 40 and from baseline to Week 64 respectively for each subject. If a subject has both

recumbent length and standing height measurements from 1.5 years prior to baseline to post-baseline period, the recumbent length will be subtracted by 0.8 cm before pooling with standing height data (<https://www.cdc.gov/nccdphp/dnpao/growthcharts/resources/sas.htm>).

An ANCOVA model will be applied on the change in growth velocity Z score from baseline to Week 40 or Week 64 to assess the difference between treatment groups. Treatment group and baseline RSS total score stratification factor will be included as independent variables, baseline Z score and age will be included as continuous covariates. The stratification factor of baseline age will not be included in the model. The estimated difference between KRN23 treatment and active control group will be provided along with 95% CI and p-value. The estimated change from baseline and its 95% CI within individual treatment groups will also be provided.

In addition, descriptive statistics of sitting height during the post-treatment period and its respective change from baseline will be provided by study visits. A listing of standing height/recumbent length and the respective Z score, percentile, growth velocity and sitting height will be provided.

8.5.4.4 Walking Ability (6MWT)

For subjects ≥ 5 years of age at the screening visit, summary statistics of total distance walked and percent of predicted 6MWT will be tabulated for each study visit for the observed measures and their respective change from baseline based on the Full Analysis Subset (Baseline age ≥ 5 years). Change from baseline of total distance walked and percent of predicted 6MWT will be assessed using the GEE approach as outlined in Section 8.5.1 with baseline measures and baseline RSS total score stratification factor included as independent variables.

A listing containing the 6MWT details will be provided. Graphs showing change in total distance walked during 6MWT and percent of predicted 6MWT will be provided by treatment group.

8.5.4.5 Patient Reported Outcomes Measurement Information System (PROMIS)

For subjects aged ≥ 5 years at screening visit, summary statistics of Pediatric Pain Interference, Physical Function Mobility and Fatigue domain scores will be reported by study visit for both observed measures and their respective change from baseline based on the Full Analysis Subset (Baseline age ≥ 5 years). Change from baseline values over time will be assessed to compare KRN23 therapy with the active control (oral phosphate/active vitamin D) using the GEE approach as outlined in Section 8.5.1 with baseline measures and baseline RSS total score stratification factor included as independent variables.

A listing of Pediatric Pain Interference, Physical Function Mobility and Fatigue domain scores will be provided.

Graphs showing change in Pediatric Pain Interference, Physical Function Mobility and Fatigue domain scores will be provided by treatment group. Cumulative Distribution Function (CDF) of change from baseline in each domain score will also be plotted by treatment group.

